8.2.2. Sample Size Sensitivity

The sample size projected for this study is based on the assumption of 54% and 80% SR rates in the placebo and ofatumumab SC treatment groups respectively. For a log rank test, the projected hazard ratio is 0.48248 (ofatumumab SC/placebo) and the projected number of subjects with SR on minimal steroid therapy is 80. If the hazard ratio is indeed 0.48248, but the response rates in both groups are lower, then more subjects will need to be enrolled in order to have at least 80 subjects with SR at the end of the study.

Table 8-1 shows the sensitivity of the sample size to the response rates in each treatment arm, assuming a hazard ratio of 0.48248.

Table 8-1 Sample Size Sensitivity

Placebo Response Rate	Ofatumumab SC Response Rate	Total Sample Size Needed for At Least 80 Responses (Assuming a 13% Dropout Rate)
0.42	0.68	166
0.44	0.70	160
0.46	0.72	154
0.48	0.74	148
0.50	0.76	144
0.52	0.78	140
0.54 ^a	0.80	136

a. Projected for the study.

The primary analysis is based on a sequential test of the 2 co-primary endpoints: time to SR on minimal steroid therapy, and duration of remission, using the method of Alosch and Huque [Alosch, 2010], described in detail in Section 8.3.6.5. In this method, a sequential testing of the co-primary endpoints is made using critical points that provide consistency results for the 2 co-primary endpoints. Two parameters were considered in the simulation: time to SR on minimal steroid therapy, and duration of remission on minimal steroid therapy. Simulations were made using an exponential time to event (time to remission, and time to flare), and using the protocol definitions of SR and duration of remission. The ranges of values for these parameters were selected to provide approximately 54% and 80% remission rates in the placebo and active groups respectively, assumed for this study.

Table 8-2 Overall Power for the Co-primary Endpoints

Parameter	Placebo	Ofatumumab SC	Overall Power
Time to remission (weeks)	28	16	95%
Duration of remission (weeks)	8	17	
Time to remission (weeks)	32	16	90%
Duration of remission (weeks)	9	17	
Time to remission (weeks)	44	20	93%
Duration of remission (weeks)	10	19	

Abbreviation: SC=subcutaneous.

Note: Based on simulation of 100 trials with 59 subjects per group.

8.2.3. Blinded Sample Size Re-estimation

The power of 90% for this study assumes that 80 subjects will have SR on minimal steroid therapy by the end of the study. This number will be monitored in a blinded way, and if necessary, more than 136 subjects will be randomized to ensure that at least 80 subjects will have SR on minimal steroid therapy at the end of the study. Because the sample size re-estimation is done in a blinded manner, based on the total number of SRs, no penalty for type-1 error inflation is warranted. The reporting and analysis plan (RAP) will specify the method of monitoring and adjustment to the sample size.

8.3. Data Analysis Considerations

Additional details of data analyses will be specified in the RAP.

8.3.1. Analysis Populations

The Intent-to-Treat (ITT) population will consist of all subjects randomized to treatment. This will be the primary population used for the efficacy analyses. The Per Protocol (PP) population will consist of those members of the ITT population who have no major protocol violations. If the PP population comprises more than 95% or less than 50% of the ITT population, it will not be analyzed. This population will be used for a confirmatory analysis of the primary efficacy endpoint and any key secondary efficacy endpoints. The primary population for safety analyses will be the safety population which will consist of all subjects who were randomized and were administered least 1 dose of investigational product. The Pharmacokinetic Population will include all subjects in the ITT population providing analyzed pharmacokinetic samples.

The Pharmacogenetic Population will include all subjects in the ITT population who consented to providing a genetics sample, provided a sample, and did not withdraw their consent.

8.3.2. Analysis Data Sets

The Observed Case dataset makes no assumptions about missing data and will lead to missing assessments being excluded from the analysis. The primary analysis dataset for the analysis of time to SR on minimal steroid therapy will be the Observed Case dataset.

Subjects who discontinue from the study before they reach SR, or finish the study without an SR will be considered as censored at their last visit. For the analysis of duration of remission on minimal steroid therapy, subjects who discontinued prior to the end of the study will be considered as not in remission from their last known visit till Week 60. For the analysis of proportion of subjects who achieve remission at Week 60, subjects who discontinued before Week 60 will be considered as not in remission.

8.3.3. Treatment Comparisons

8.3.3.1. Primary Comparisons of Interest

The primary comparison of interest of this study is between placebo and ofatumumab SC on time to SR on minimal steroid therapy, and duration of remission on minimal steroid therapy. These comparisons will be made using the sequential method of Alosch and Huque [Alosch, 2010], described in Section 8.3.6.5.

8.3.3.2. Other Comparisons of Interest

Secondary comparisons of interest will be made between placebo and ofatumumab SC on the secondary endpoints, sequentially in the order presented in Section 6.2.2, only if the 2 co-primary endpoints have been found significant. All tests will be done at two-sided 0.05 level of significance. To protect against an inflation of type-1 error, if any of the comparisons are found not statistically significant, no subsequent tests of significance will be performed on the secondary endpoints.

Comparisons of interest will be made between placebo and ofatumumab SC on the other endpoints.

8.3.4. Interim Analysis

An interim analysis for futility will be conducted when 60 events of SR on minimal steroid therapy have been observed. The analysis will be conducted by an unblinded statistician not involved in the conduct of the study and results will be presented to the IDMC. A conditional power analysis will be conducted based primarily on projecting the observed trend of the difference between ofatumumab and placebo in time to remission on minimal steroid therapy. If the analysis indicates that the conditional power for a positive outcome for time to remission on minimal steroid therapy ($p < 0.025$ one-sided) is less than 30%, the IDMC will communicate to designated Sponsor's representatives that the study is unlikely to meet its primary objectives. The Sponsor may evaluate additional information such as pharmacokinetics and pharmacodynamics and make a final decision regarding continuation of the study.

If enrollment is substantially slower than anticipated and/or the rate of SRs is much smaller than projected, consideration will be given to performing the interim analysis for futility at an earlier time point. If a decision is made to perform an early interim analysis, the IDMC will be notified of this decision and preparation will be made for an unscheduled IDMC meeting. After review of the interim data, the IDMC may:

- Recommend continuing the study as planned.

- Determine that continuation of the study is unlikely to reach a successful conclusion on the basis of the slow enrollment and/or low rate of remissions and thus recommend stopping the study early for futility.

The interim analysis will not be used to stop the study early for a positive outcome; therefore, no adjustment to the final analysis type-1 error is indicated. Details of the interim analysis will be specified in the IDMC charter, as well as in the RAP.

8.3.5. Reporting Time Points

Reporting of the study will occur at 2 time points:

- Sponsor unblinding for analyses to support regulatory submissions will occur after all subjects have completed the Week 60 visit (primary analysis time point) or been withdrawn from the Treatment Period; all data will be cleaned and the database up to this time point will be frozen.
- The final analysis will occur after the last subject's last visit in the Individualized Follow-up Period (ie, after all subjects have completed the full study or been withdrawn prematurely); data from the Individualized Follow-up Period will be reported in an addendum to the clinical study report.

8.3.6. Key Elements of Analysis Plan

8.3.6.1. Missing Data

The co-primary efficacy endpoint of time to SR on minimal steroid therapy will be analyzed using the ITT Observed Case dataset. Subjects who discontinue from the study before the end of the study, or reach their last planned visit without achieving SR on minimal steroid therapy, will be censored in the analysis at their last visit. If discontinuations from the study are for reasons that are independent of this endpoint, then this analysis is not biased. If discontinuations are for reasons that are correlated with the endpoint, the statistical test may be biased, particularly, if 1 of the treatment arms has a markedly larger number of discontinuations. An early discontinuation of a subject before achieving an endpoint may have an unduly favorable bias towards the treatment arm that has more discontinuations, since the time-to-event analysis uses the shortened exposure time due to the discontinuation. One can make an assumption that if the discontinuation is due to lack of efficacy, or for safety reasons, that subject would not have achieved the endpoint had the subject continued to the end of the study. Therefore, as a sensitivity analysis, subjects who discontinued before the end of the study will be considered as censored at the end of the study rather than at their last visit. For the other co-primary endpoint, duration of remission on minimal steroid therapy, subjects who discontinued before the end of the study will be considered as not in remission from the last known visit till Week 60.

For the secondary endpoint of the proportion of subjects in remission on minimal steroid therapy at Week 60, subjects who discontinued prior to Week 60 will be considered as not in remission at Week 60.

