6.2.1. Primary Efficacy Endpoints

[figure not shown]
Two co-primary efficacy endpoints will be evaluated:

- Time to sustained remission (SR) on minimal steroid therapy (defined as time from randomization to the time the subject initially tapered his/her oral prednisone/prednisolone dose to ≤ 10 mg/day and maintained ≤ 10 mg/day of oral prednisone/prednisolone with no new or nonhealing lesions for ≥ 8 weeks AND maintained that status until Week 60).
- Duration of remission on minimal steroid therapy (defined as total time [sum] of all periods of remission while on minimal steroid therapy [oral prednisone/prednisolone dose of ≤ 10 mg/day] up to Week 60).

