8.2. Study Design Considerations

8.2.1. Sample Size Assumptions

Assuming that the proportion of subjects achieving SR on minimal steroid therapy status is 54% and 80% in the placebo and the ofatumumab SC groups, respectively [Beissert, 2010], with proportional hazards across the various strata, a sample size of 68 subjects per group will give $\geq 90\%$ power for a statistically significant difference between the two groups in time to SR on minimal steroid therapy, using a two-sided 0.05 level of significance. Note that for the purpose of sample size calculation of time to SR, “survival” means: “Not in SR”, and hence $(100-54=)$ 46%, and $(100-80=)$ 20% are the survival rates for the placebo and ofatumumab SC treatment groups respectively needed to calculate sample size for the log-rank test. The study is designed to detect a hazard ratio of 0.48248 (median time to response on ofatumumab SC/median time to response on placebo). It is assumed that no more than 13% of the subjects in both groups will be lost to follow-up before their Week 60 visit. With the projected 54% and 80% SR rates in the placebo and active groups respectively, a total of approximately 80 subjects with SR in both treatment groups combined are needed at the end of the study. Because this study has 2 co-primary efficacy endpoints, an evaluation of the overall power to detect at least one significant endpoint was made using simulations. The analysis proposed for the

co-primary endpoints is a sequential test based on the method of Alosch and Huque [Alosch, 2010]. Results of the simulations are displayed in Table 8-2.

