8.3.6.5. Efficacy Analyses

Graphical displays and tables will present and summarize all efficacy measures over the course of the study. Means, SDs, medians, maximum, minimum, and number of subjects will summarize continuous data. Categorical data will be summarized by counts and percentages. Confidence intervals (Cis) (95%) and p-values will be displayed where applicable.

Primary Endpoint Analyses

Baseline prednisone/prednisolone dose and disease duration will be used to stratify all primary and secondary analyses. The primary analysis for the co-primary endpoints will use the ITT population.

The co-primary efficacy endpoint of time to SR on minimal steroid therapy by Week 60 will be analyzed using a log-rank test stratified by baseline prednisone/prednisolone dose and disease duration strata. Subjects who discontinue prematurely (prior to Week 60) will be censored at the time they discontinued. Subjects who reach Week 60 without remission will be censored at their last visit. Calculation of time to SR will be made from randomization date to the first time the subject was in remission for 8 consecutive weeks while on minimal steroid therapy and sustained that remission until Week 60.

The co-primary endpoint of duration of remission on minimal steroid therapy will be analyzed using a rank analysis of covariance (ANCOVA) [Stokes, 2000], with treatment as a main effect, and baseline prednisone/prednisolone dose and disease duration strata as covariates. If a subject went into remission, then relapsed, and then went into remission

again (or possibly more than 2 episodes of remission), the duration of remission will be the total time (sum) of all periods of remission while on minimal steroid therapy up to Week 60. If a subject discontinued the study prior to Week 60, the subject will be considered as not in remission from the last known visit till Week 60.

To protect the overall type-1 error at 0.05 (one-sided 0.025), the analysis of the co-primary endpoints will follow the procedure proposed by Alosch and Huque [Alosch, 2010]. In this procedure, a consistency criterion is applied, so that the co-primary endpoints can be deemed significant only if one of the following events occur:

1. The time to SR on minimal steroid therapy is significant at one-sided 0.02. If significant, then duration of remission on minimal steroid therapy is tested at one-sided 0.025.

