9.1.2. Missing Data

9.1.2.1. Co-primary Efficacy Endpoints

The co-primary efficacy endpoint of time to SR on minimal steroid therapy will be analyzed using the ITT. Subjects who discontinue from the study before the end of the study (Wk 60), or reach their last planned treatment visit without achieving SR on minimal steroid therapy, will be censored in the analysis at their last visit. Subjects who discontinue prematurely (prior to Week 60) will be censored at the time they discontinued. Subjects who reach Week 60 without remission will be censored at their last visit.

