11.1. Primary Efficacy Analyses

11.1.1. Time to SR on Minimal Steroid Therapy by Week 60

The co-primary efficacy endpoint of time to SR on minimal steroid therapy by Week 60 (as defined in Section [2.2.1](#)) will be analyzed using a log-rank test stratified by baseline prednisone/prednisolone dose and disease duration strata. Subjects who discontinue prematurely (prior to Week 60) and who have not achieved remission upon discontinuation will be censored at the time they discontinued. Subjects who reach Week 60 without remission will be censored at the date of their last visit.

For subjects achieving remission, time to SR on minimal steroid therapy will be derived as: [(the date on which the subject initially tapered his/her oral prednisone/prednisolone dose to ≤ 10 mg/day and maintained ≤ 10 mg/day of oral prednisone/prednisolone with no new or nonhealing (established) lesions for ≥ 8 weeks and maintained that status until Week 60) – (the date of randomization)] + 1 day.

A summary table presenting the Kaplan-Meier estimates for the time to SR and 95% CI at Week 4, week 8, Week 12 etc. for each of the treatment groups and p-value for the treatment difference, using the 2-sided log-rank test indicated above will be presented for the ITT population and PP population (if criteria are met as discussed in Section [11](#)).

For the covariate analysis, a summary table computing hazard ratio and 95% CI for the hazard ratio and the p-value using the Cox proportional hazards model discussed in Section [8.2](#), will be presented for the full model for the ITT population.

A Kaplan-Meier plot of time to SR on minimal steroid therapy will be constructed for each treatment group for the ITT population.

11.1.2. Duration of Remission on Minimal Steroid Therapy by Week 60

The co-primary endpoint of duration of remission on minimal steroid therapy will be analyzed using a rank ANCOVA [[Stokes 2000](#)], with treatment as a main effect, and baseline prednisone/prednisolone dose and disease duration strata as covariates. If a subject discontinues the study prior to Week 60, the subject will be considered as not in remission from the date of the last known study visit until Week 60.

For subjects who complete the study without experiencing any periods of remission, duration of remission on minimal steroid therapy will be 0 days.

One Period of Remission

For subjects who experience one period of remission on minimal steroid therapy that:

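### Time to sustained remission erases remissions in anyone who leaves before Week 60, so outcome-independent dropout still lowers estimates and power, and distorts type I error when dropout differs by arm

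*Protocol*

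**What the plan says.** **Event.** Time to SR is a co-primary endpoint (Protocol 6.2.1). The subject must taper to 10 mg/day or less, have no new or nonhealing lesions for at least 8 weeks, "AND maintained that status until Week 60". The event date lies well before Week 60. Section 6.2.1 uses the time of the taper; Protocol 8.3.6.5 uses the first completion of 8 consecutive weeks, again only if the subject "sustained that remission until Week 60".

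**Censoring.** Protocol 8.3.6.5: "Subjects who discontinue prematurely (prior to Week 60) will be censored at the time they discontinued". SAP 9.1.2.1 repeats that rule and also says that subjects who leave before Week 60 "will be censored in the analysis at their last visit".

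**Claim about bias.** Protocol 8.3.6.1: "If discontinuations from the study are for reasons that are independent of this endpoint, then this analysis is not biased". For reasons correlated with the endpoint, it warns of bias in favour of the arm with more discontinuations. Its one sensitivity analysis has leavers "considered as censored at the end of the study rather than at their last visit".

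**Passages that differ.** Protocol 8.3.2 ties censoring to leaving before SR is reached. SAP 11.1.1 covers only leavers before Week 60 "and who have not achieved remission upon discontinuation will be censored at the time they discontinued" and gives leavers in remission no rule. The SAP does not carry the sensitivity analysis forward.

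**Power.** Under Protocol 8.2.1, "a sample size of 68 subjects per group will give" at least 90% power for time to SR, with SR rates of 54% and 80% and at most 13% lost before Week 60.

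**The concern.** Independent censoring protects a log-rank test only if an event that happens before the subject leaves is recorded. Here it is not. Take a subject in remission from Week 24 who moves away at Week 50. The event would be dated about Week 24 (or Week 32, on the 8-week-completion rule). Because Week 60 is never reached, the subject is instead counted as at risk and not in SR until Week 50, then censored. Whether a remission counts depends on staying to the end, so the censoring is informative by construction, whatever the reason for leaving.

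This affects a co-primary test. The study was terminated early with 69 randomised (SAP 1 and 5), so subjects leaving before Week 60 may be common, and administrative leaving is just the case that the protocol treats as harmless.

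**Working it through.** **1. The plan's own figures (Protocol 8.2.1, 8.2.2).**
- Hazard ratio: ln(0.46)/ln(0.20) = 0.48248, as stated; as a remission hazard ratio (ofatumumab/placebo), 1/0.48248 = 2.07.
- Events for 90% power, two-sided 0.05 (Schoenfeld): 4 × (1.960 + 1.282)² / (ln 0.48248)² = 79.1, so 80, as stated.
- Expected events: 136 × 0.87 × (0.54 + 0.80)/2 = 79.3. The calculation therefore takes no events from the 13% lost, in line with the censoring rule. The event count and the 136 subjects are not in error. What is missing is the effect of the rule on the hazard ratio.

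**2. Direction, without simulation.** Early in follow-up, the observed hazard in an arm is the true hazard times roughly P(stay to Week 60)/P(stay to t).
- Equal dropout, no drug effect: observed time and event status have the same distribution in both arms, so the log-rank size holds.
- Equal dropout, real effect: unrecorded remissions accumulate faster in the risk set of the better arm, so the hazard ratio drifts toward 1.
- Unequal dropout, no effect: the factors differ. At 25% placebo and 5% ofatumumab the starting ratio is 0.95/0.75 = 1.27, in favour of ofatumumab.

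**3. Simulation.** 68 per arm, 8,000 trials per scenario, unstratified log-rank. Time to SR is exponential with the stated Week 60 rates; dropout is exponential and independent of it. The documents give no dropout by arm, so every split is an assumption. The benchmark counts an SR when it is reached.

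Planned effect (54%/80%):

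| Dropout per arm | Rule | Hazard ratio | Kaplan-Meier SR at Week 60 | Power |
|---|---|---|---|---|
| 13% | plan | 2.005 | 51%/76% | 0.870 |
| 13% | benchmark | 2.07 | 54%/80% | 0.915 |
| 13% | leavers censored at Week 60 | 1.91 | 47%/70% | 0.819 |
| 25% | plan | 1.95 | 48%/71% | 0.789 |
| 25% | benchmark | 2.07 | 54%/80% | 0.912 |

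Check by formula: the plan rule gave 79.2 events on average. Power = Φ(√79.2/2 × ln 2.005 − 1.960) = Φ(1.135) = 0.87. With the unattenuated 2.07 it is Φ(1.28) = 0.90. The attenuated hazard ratio accounts for the shortfall.

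No effect (54% in both arms), one-sided rejection, nominal 0.025:

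| Dropout placebo/ofatumumab | Rule | Favouring ofatumumab | Favouring placebo |
|---|---|---|---|
| 13%/13% | plan | two-sided total 0.048 | |
| 13%/5% | plan (separate run) | about 0.046 | |
| 8%/18% | plan | 0.010 | 0.048 |
| 25%/5% | plan | 0.096 | 0.005 |
| 25%/5% | benchmark | 0.024 | 0.024 |
| 25%/5% | leavers censored at Week 60 | 0.237 | |

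The arm with more dropout is penalised. The sensitivity analysis pushes the same way, harder: at 25%/5% with no effect, the hazard ratio is 1.19 under the plan and 1.38 with leavers censored at Week 60.

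**The case against.** **Size holds under equal dropout.** A reader might infer that the log-rank test is invalid whenever anyone leaves. It is not. With equal, outcome-independent dropout, repeat runs gave 0.023 to 0.029 per side. False positives need dropout to differ by arm.

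**Leavers are not always excluded.** A reader might also infer that leavers can never be events under either document. That is true of Protocol 8.3.6.1 and 8.3.6.5 and of SAP 9.1.2.1. SAP 11.1.1 leaves the question open; if it were completed so that leavers in remission are events, the erasure would go. The conflict between passages is therefore part of this point.

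**The larger figures rest on assumed dropout.** The plan allows at most 13% in both groups. Within that limit, 13%/5% gives about 0.046, not 0.10. This stands.

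**The benchmark is not a usable analysis of SR**, because a leaver's Week 60 status is unknown. It measures the loss and is not a proposed replacement.

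**Counting leavers in remission as events need not bracket the truth.** Some would have relapsed. Assume remission onset in 75%/85% (placebo/ofatumumab), sustained in 72%/94% of those: 0.75 × 0.72 = 0.54 and 0.85 × 0.94 = 0.80, the plan's rates. The true hazard ratio was 2.00. At an assumed 50% dropout, plan scoring gave 1.77 and the alternative 1.84; at 25%, 1.89 and 1.92. A further run with assumed differential relapse and 50% dropout gave 1.72 and 1.86. Both fall below the truth each time.

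**The protocol's direction warning concerns outcome-related leaving.** That is fair. The erasure works the opposite way, and if both operate the net direction is unknown.

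**Conclusion.** The protocol's assurance is wrong and should be corrected. Under its censoring rule, independent dropout gives SR estimates that are too low (51%/76% against 54%/80% at the planned 13%), a hazard ratio nearer 1, and time-to-SR power of about 87%. If dropout differs by arm, the test works against the arm with more dropout: one-sided size is about 0.046 at an assumed 13%/5% and about 0.09 to 0.10 at an assumed 25%/5%. The sizes rest on exponential times and the assumed dropout splits; the direction does not rest on the exponential form.

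The documents do not support moving the main conclusion to time to first remission. That is a secondary endpoint, and the Amendment 7 entry in Protocol Appendix 15 records that the sponsor had already unblinded treatment assignments after termination.

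This should be fixed but is not critical. The SAP sets the sample-size sections aside, p-values are nominal without multiplicity control, and time to first remission is already planned. The duration co-primary credits remission up to a leaver's last visit (SAP 11.1.2).

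**What to change.** - Replace the sentence in Protocol 8.3.6.1 with: *Independent dropout does not make this analysis unbiased: SR estimates are too low, the hazard ratio is attenuated, and type I error is distorted if dropout differs by arm.*
- Reconcile Protocol 8.3.2, 8.3.6.1 and 8.3.6.5 with SAP 9.1.2.1 and 11.1.1 into one explicit rule for leavers in remission.
- Restate the protocol's time-to-SR power as about 87%, under exponential assumptions.
- Keep time to SR as co-primary. Add a supportive log-rank run in which leavers who are in remission of at least 8 weeks on 10 mg/day or less at their last visit are events at their remission date. Do not describe the two runs as bracketing the answer.
- Tabulate leavers in remission by arm.
- Present time to first remission (SAP 11.2.2) as supportive evidence, not as a replacement, with a supportive run that dates the event when the 8 weeks are completed. That event is known on its date, so censoring leavers at their last visit does not erase it.

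Cost: wording, a slightly lower stated power, one table, and supportive runs on existing data.
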